4.0 Background

Gliomas represent the most common primary brain tumor in the adult population. Malignant gliomas include anaplastic astryocytoma (AA) and glioblastoma multiforme (GBM) and have an annual incidence of 3 to 4 per 100,000, with over 80% of these being GBMs [12]. The standard treatment for glioblastoma is maximal safe resection followed by involved-field radiation. A pooled analysis of six randomized trials demonstrated that there is a significant survival benefit to the addition of radiation therapy after surgical resection [13]. Historically outcomes have been quite poor with median survival of less than one year for GBM [12].

Recently, combined modality treatment including the addition of concurrent and/or adjuvant temozolomide has resulted in significant improvement in outcomes for glioblastoma patients [2, 14]. Stupp et. al. demonstrated a 2 year overall survival (OS) rate of 27.2% with concomitant and adjuvant temozolomide as compared to a 10.9% 2 year OS rate with radiation alone [2]. This response was found to be durable at 5 years of follow up. Indeed, patients with favorable prognostic categories such as MGMT promoter methylation had even better survival outcomes. With improved outcomes and longer survival an increasing number of patients are at risk for secondary adverse effects from radiation treatment, particularly cognitive decline.

Cognitive function has been increasingly recognized as a key primary outcome measurement following cranial radiotherapy. Several studies have suggested that in high grade glioma patients tumor progression was the dominant cause of cognitive decline [15-17]. However, these studies were done in the era prior to the introduction of combined modality treatment when median survival was less than one year. While tumor progression is a key factor in cognitive function, prolonged survival with combined modality treatment will also lead to an increasing number of patients who develop treatment related late toxicity.

Data in low grade glioma patients suggests that the amount of brain exposed to radiation as well as the dose of radiation has a significant impact on cognitive function [3, 4, 18]. Similarly, metastatic brain cancer patients receiving stereotactic radiation have improved cognitive outcomes compared to patients treated with whole brain radiation therapy [19]. This has led to an increased interest in using more focused radiation therapy for glioblastoma.

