9.0 Evaluation During Study

- 9.1 A history and physical exam will be performed at two month intervals for a total of 24 months of follow up after the completion of the assigned treatment (±30 days). Note the first evaluation after radiotherapy will frequently be performed approximately 4 weeks after completion of radiotherapy and then the study will continue with history and physical exam at 2 month intervals.
- 9.2 Neuropsychological testing will be performed at each follow up visit, up to two years post radiation treatment. Reasonable effort will be made to complete this testing prior to patients meeting with their physicians and receiving information about the status of their disease.
- 9.3 Routine MR imaging of the brain performed with and without contrast will be obtained at each follow up visit at 2 month intervals (±30 days) until recurrence or up to two years post radiation treatment. Note the first evaluation after radiotherapy will frequently be performed approximately 4 weeks after completion of radiotherapy and then the study would continue with follow-up imaging at 2 month intervals. These post-treatment scans will be analyzed and compared to baseline scans for identification of regions demonstrating changes in contrast enhancement including size, heterogeneity and rim thickness. Qualitative estimation of associated T2-FLAIR changes will also be evaluated. Early stages of malignant gliomas have demonstrated decreased water diffusion. Routinely obtained diffusion weighted images and reconstructed ADC maps will be analyzed to see if there is a difference between pre- and various post-treatment scans. Based on contrast enhancing imaging features, manually selected regions of interest on ADC maps will be

quantitatively analyzed, normalized to contralateral unaffected brain parenchyma and compared on serial scans. Similarly DTI maps and cognitive functions will be correlated.

- 9.4 Medication usage (specifically steroid dose, narcotic pain medications, antiepileptic agents, psychostimulants) will be recorded. Steroid doses will be adjusted based on clinical and radiographic criteria.
- 9.5 Requirements for more frequent evaluation will be documented. Data on unscheduled follow-ups will also be documented.

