10.2.1.3 Progressive Disease (PD): Defined as any of the following 1) \geq 25% increase in the sum of the products of perpendicular diameters of enhancing lesions compared with the smallest tumor measurement obtained either at baseline (if no decrease) or best response, on stable or increasing dose of corticosteroids; 2) significant increase in T2/FLAIR nonenhancing lesion on stable or increasing doses of corticosteroids compared with baseline or best response not caused by comorbid events (i.e. radiation therapy. demvelination, ischemic injury postoperative changes); 3) any new lesion; 4) clear clinical deterioration not attributable to other causes apart from tumor (i.e. seizures, medication adverse effects, complications of therapy, cerebrovascular events, infection, or decrease in corticosteroid dose); 5) failure to return for evaluation due to death or deteriorating condition; 6) clear progression of non-measurable disease.

When making the diagnosis of progressive disease it is import to recognize the possibility of pseudo-progression, especially if the patient is clinically stable. In those situations, treatment should continue and status of local control should be evaluated with a repeat interval scan. If the subsequent scan confirms progression then the date of progression should be backdated to the original scan suggesting progression.

- 10.2.1.4 Stable Disease (SD): Requires all of the following 1) does not qualify for complete response, partial response, or progression; 2) stable FLAIR/T2 lesions on corticosteroid dose no greater than at baseline; 3) clinical status stable.
- 10.2.1.5 For local control, PD is considered local failure, or stable disease with deterioration of the neurological examination with a grade III or worse toxicity on the CTCAE v.4.0 scale (see Appendix). All others (CR, PR, asymptomatic SD) are deemed success.
- 10.2.2 Overall survival will be measured from registration until death. After 2 years of follow-up event monitoring will be used.
 - 10.2.2.1 Patients with unknown vital status will be censored at the date of last visit or MRI scan.
- 10.2.3 Quality of life will be measured at each two month interval follow up visit out to two years using the EORTC QLQ C30/BN20 and the MD Anderson Symptom Inventory Brain Tumor (MDASI-BT).

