- 12.3 Primary Analysis: The analysis will be performed on the intention-to-treat principle. Considering those patients who are not evaluable as treatment failures. We will use the methods of Gooley et al. [52]to estimate the cumulative incidence of cognitive failure in each treatment arm, considering progressive disease and death before cognitive failure as competing events. We will estimate the cumulative incidence of cognitive failure at 4 months with 95% confidence intervals. We will use the methods of Fine and Gray [53]to test for a difference between treatment arms with respect to the cumulative incidence of cognitive failure, considering progressive disease and death before and death before and death before cognitive failure as competing events. We will use the methods of Fine and Gray [53]to test for a difference between treatment arms with respect to the cumulative incidence of cognitive failure, considering progressive disease and death before cognitive failure as competing events. Our model will include treatment arm and the stratification factors used at randomization.
- 12.4 Secondary Analysis:

We will repeat the primary analysis on only those patients considered evaluable. All the secondary analyses described below will be performed using all patients as well as using only evaluable patients. We will estimate the cumulative incidence of local failure using the methods of Gooley et al. considering death as a competing event. We will model the time to local failure using the methods of Fine and Gray to test for differences between treatment arms, considering death as a competing event. Our model will include treatment arm and the stratification factors used at randomization, as well as selected dosimetric parameters. We will similarly analyze time to distant failure.

We will use the product limit estimator of Kaplan and Meier [54] to estimate overall survival stratified by treatment arm. We will also use Cox proportional hazards regression [55] to model overall survival as a function of treatment arm and the stratification factors used at randomization.

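### Overall survival is censored at the last visit or MRI rather than the date last known alive, although event monitoring continues after both have ended

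*Combined protocol and SAP*

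**What the plan says.** Section 10.2.2 defines the endpoint: "Overall survival will be measured from registration until death". It continues: "After 2 years of follow-up event monitoring will be used". Section 10.2.2.1 then gives the only censoring rule for survival: "Patients with unknown vital status will be censored at the date of last visit or MRI scan".

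Section 9 sets when visits and scans occur. The clinic schedule in 9.1 reads: "A history and physical exam will be performed at two month intervals for a total of 24 months of follow up after the completion"; the reference point is the end of radiotherapy. Under 9.3, MRI continues "until recurrence or up to two years post radiation treatment".

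Section 12.4 uses Kaplan-Meier "to estimate overall survival stratified by treatment arm" and Cox regression "to model overall survival as a function of treatment arm and the stratification factors used at randomization". It has no censoring rule that would override 10.2.2.1.

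The documents do not describe event monitoring (method, frequency, or whether contacts with living patients are dated), state a loss rate for survival, or set a date for the survival analysis.

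**The concern.** The plan opens a follow-up channel after 2 years and then leaves it out of the censoring rule. Take two patients, both contacted alive at month 40. One dies at month 44 and monitoring finds the death: all 44 months count. The other cannot be reached after month 41: vital status is unknown, so the patient is censored at the last visit or scan, about month 24 unless there was a later off-protocol one. The first keeps 20 months of late follow-up (44 − 24). The second loses 16 months of time known alive (40 − 24).

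Whether late person-time is kept therefore depends on how the patient's course ended, which makes the censoring informative. What is at stake is the late part of the survival curve, that is, the longer-term survivors whose risk of late effects motivates the trial in section 4. The comparison of survival across MCP classes in 12.4 would presumably inherit the same times.

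**Working it through.** **Plan's own figure.** There is none to reproduce. The events, power and duration in 12.2 concern cognitive failure, not survival.

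**Direction relative to last-known-alive censoring.** Each Kaplan-Meier factor is 1 − d/n. Both rules count the same deaths d at the same times. The present rule moves some censoring dates earlier and none later, so n is never larger. Every factor, and hence the curve, is equal or lower.

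**Inputs for size.**
- From section 4: "a 2 year overall survival (OS) rate of 27.2% with concomitant and adjuvant temozolomide". A constant hazard gives −ln(0.272)/2 = 0.65 per year.
- Assumed: death hazard after month 24 of 0.25, 0.40 or 0.65 per year; loss of 5%, 10% or 20% per year after month 24, unrelated to death; administrative end spread evenly over months 36 to 84; last visit at about month 24 from registration. Visits actually run to 24 months after radiotherapy, so the effect starts slightly later.

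**Formula.** Let h be the death hazard and l = −ln(1 − annual loss) the loss hazard. If everyone were followed to death or loss, the proportion at risk at time s after month 24 under the present rule would be [h/(h + l)]·exp(−(h + l)s), and deaths would occur at rate h·exp(−(h + l)s). The estimated hazard would be h + l: losses act like deaths. An administrative end puts it between h and h + l.

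**Results.** Simulation of 400,000 patients per setting, survival in %:

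| Hazard/yr | Loss/yr | True at 36 / 48 / 60 months | Present rule |
|---|---|---|---|
| 0.25 | 5% | 21.1 / 16.5 / 12.9 | 20.7 / 15.8 / 12.1 |
| 0.25 | 20% | 21.2 / 16.5 / 12.9 | 19.1 / 13.7 / 10.0 |
| 0.40 | 10% | 18.3 / 12.2 / 8.2 | 17.1 / 10.9 / 7.0 |
| 0.65 | 5% | 14.2 / 7.4 / 3.9 | 13.7 / 6.9 / 3.5 |
| 0.65 | 20% | 14.1 / 7.4 / 3.8 | 11.9 / 5.4 / 2.5 |

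Over all settings the shortfall is 0.4 to 2.9 points. Censoring at last contact is within 0.1 point of the truth. Check on the middle row: l = −ln(0.9) = 0.105. The true value is 27.2% × exp(−0.80) = 12.2% and the limit is 27.2% × exp(−2 × 0.505) = 9.9%; 10.9% lies between.

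At 30% loss a year, with administrative end at months 36 to 72, the shortfall is larger. At hazard 0.65, 14.2% reads 11.0% at 36 months (3.2 points) and 7.4% reads 4.8% at 48 months (2.6 points). At half that hazard, 14.2% reads 10.4% at 48 months (3.8 points).

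**If deaths are missed instead.** Suppose 10% to 30% of deaths after month 24 go unrecorded and there is no other loss. At 48 months the present rule reads 0.4 to 1.8 points too high, and last-contact censoring 0.8 to 3.3 points too high (largest case: true 7.4%, 8.7% against 10.7%).

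**Arm comparison.** With no true effect and assumed loss of 10% a year in one arm and 30% in the other, the Cox hazard ratio moves from about 1.00 to 1.04. With equal loss it stays at about 1. Even with 90 deaths, the standard error of the log hazard ratio is √(4/90) = 0.21, against ln(1.04) = 0.04.

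**Scale in this trial.** 90 × 0.272 = 24 patients at risk at month 24. At a true 48-month survival of 7.4%, the binomial standard error is √(0.074 × 0.926/90) = 2.8 points for 90 patients and 3.9 points for 45, before censoring widens it.

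**The case against.** The strongest objection is that the documents never describe event monitoring. If it records only deaths, there is no dated contact to discard. A visit is not limited to protocol visits, so later clinic attendance or scans could advance the censoring date. Patients with known vital status are outside the rule. All of this stands: the size of the effect depends on unstated facts, and with no loss there is no effect. It does not remove the defect in the wording, which names two sources and omits the one the plan relies on after 2 years.

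A reader might infer that survival is biased downward whatever happens. The documents do not support that. Patients may become unreachable because they are dying, and if those deaths are missed the present rule overstates survival, though less than last-known-alive censoring does. That is one error partly offsetting another, in an amount nobody can know beforehand; it is not a reason to keep the rule.

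A reader might also infer serious distortion before month 24, because MRI stops at recurrence. The rule takes the last visit or MRI, and the visits in 9.1 and the cognitive testing in 9.2 run to two years with no stop at recurrence.

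Finally, the only analysis time given is about 41 months, for the primary endpoint. At 2 patients a month, 2 × (41 − 24) = 34 would have been enrolled more than 24 months earlier, and 34 × 0.272 is about 9 still at risk. Survival at 48 months could not be estimated then. The figures above matter for a later survival analysis, which event monitoring implies but the plan does not date.

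**Conclusion.** The point holds in a limited form. Read literally, 10.2.2.1 makes the censoring date depend on outcome and does worse than last-known-alive censoring when loss is unrelated to death. The shortfall is then about 0.4 to 2.9 percentage points at 36 to 60 months for losses of 5% to 20% a year, and 2.6 to 3.8 points in the 30% examples. These figures rest on assumed loss rates, late hazards and follow-up windows; only the 27.2% comes from the documents. If late deaths are missed, the net bias can be upward under either rule.

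The effect is confined to the late curve of a secondary endpoint and is mostly below sampling error. The primary endpoint and survival to about 2 years are essentially unaffected. It would go too far to say that the rule creates a survival difference between arms: this needs unequal loss, for which the documents give no reason, and even 10% against 30% a year gives a hazard ratio of only about 1.04. The change is worth making because it is simple and removes an avoidable asymmetry.

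**What to change.** Replace 10.2.2.1 with: *Patients not known to have died by a common data cut-off date will be censored at the last date known alive on or before that date, from visits, MRI, cognitive tests or event-monitoring contacts, ascertained in the same way in both arms.* Report loss to follow-up for survival by arm.

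The cost is small but not nil. Dates of contact with living patients must be recorded during event monitoring, which the documents do not say is done. If late deaths are missed, the estimate will be higher than under the present rule: at 48 months by 0.2 points (17.2% against 17.0%) to 2.0 points (10.7% against 8.7%) in the settings above. The common cut-off, equal ascertainment and reporting of loss by arm are there to limit that risk and make it visible.

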3.0 Objectives

3.1 Primary Objectives

- 3.1.1 To assess whether treatment with IMPT results in longer time to cognitive failure compared with IMRT. Cognitive failure is defined as the first cognitive failure on any of the following six cognitive outcome variables: Hopkins Verbal Learning Test Revised (HVLT-R) Total Recall, HVLT-R Delayed Recall, HVLT-R Delayed Recognition, Controlled Oral Word Association (COWA), Trail Making Test (TMT) Part A or Part B.
- 3.2 Secondary Objectives
 - 3.2.1 To determine local control in the brain post radiation treatment.
 - 3.2.2 To determine overall survival in each treatment arm.
 - 3.2.3 To assess quality of life measured at two month intervals for a total of two years post-radiotherapy for both treatment arms.
 - 3.2.4 To assess the pattern of cognitive change in memory at two month intervals for two years post-treatment as well as executive function and processing speed.
 - 3.2.5 MRI diffusion weighted images (DWI) and reconstructed apparent diffusion coefficient (ADC) maps will be analyzed to see if there is a difference between pre- and post-treatment scans. These will also be analyzed for differences between the two treatment modalities.
 - 3.2.6 To evaluate if diffusion tensor imaging (DTI) correlates to the cognitive changes and if there are differences between the two treatment modalities.
 - 3.2.7 To assess the pre-treatment factors of recursive partitioning analysis (RPA) class and mini mental status examination (MMSE) in the predictive determination of local and distant control and cognitive outcome in each treatment arm.
 - 3.2.8 To assess the correlation between location of primary lesion, total volume of intracranial disease, and cognitive outcome in each treatment arm.
 - 3.2.9 To determine the relationship between MGMT promoter methylation status and cognitive and local control outcomes.
 - 3.2.10 To document and descriptively compare post-treatment adverse side effects between the two treatment arms.
 - 3.2.11 To determine the relation between dosimetric parameters and cognitive and local control outcomes.
- 3.3 Correlative objectives
 - 3.3.1 To determine if Apo E (i.e., Apo E2, Apo E3, and Apo E4) genotyping may prove to be a predictor of radiation induced neurocognitive decline (or neuro-protection).
 - 3.3.2 To determine if inflammatory markers (i.e., IL-1, IL-6, and TNF- α) may prove to be predictors of radiation induced neurocognitive decline.

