Decreased dosage to critical normal brain tissues has been suggested to translate into improved cognitive function. Merchant et al. compared dose characteristics for four types of common childhood brain tumors treated using conformal protons versus photons and in dosevolume modeling systems found that proton plans resulted in better cognitive outcomes. Specific advantages included decreased IQ loss, less cochlea damage, and decreased endocrine effects[10]. The study of long term benefit of proton therapy in pediatric patients will require years of follow up but the preliminary results are encouraging. Similarly Arvold et al. modeled doses for protons versus photons in the treatment of benign meningiomas. They showed that protons could decrease the risk of radiation associated secondary malignancies by half and that lower doses to critical structures supporting cognitive functions such as memory including the temporal lobe and hippocampus could be achieved with proton plans [21].

While the theoretical dosimetric advantages of proton plans are intriguing we do not have randomized data comparing cognitive outcomes in glioblastoma patients treated with these two modalities. We hypothesize that IMPT will result in improved cognitive outcomes. In this trial we propose to address this question by prospectively randomizing patients with glioblastoma to treatment with IMRT versus IMPT. Patients will be stratified by RPA class, Mini Mental Status Examination score (21-26 vs. 27-30)[17], and age (less than 65 vs. 65 and older). These factors are known to have prognostic significance. The primary endpoint will be time to first cognitive failure on any of the following six cognitive test variables: HVLT-R Total Recall, HVLT-R Delayed Recall, HVLT-R Delayed Recognition, COWA, and TMT A or B. Secondary endpoints will include local control and overall survival outcomes as well as quality of life. Addressing this question in a prospective randomized fashion can be accomplished at MDACC given the high volume of cancer patients with glioblastoma treated at our center.

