7.0 Treatment Plan

- 7.1 Eligible patients will be randomized in equal numbers to each treatment arm using CORe. Randomization will be stratified using the following factors:7.1.1 RPA class (III or IV vs. V)
 - 7.1.2 Mini Mental Status Examination score (21-26 vs. 27-30)
 - 7.1.3 Age (less than 65 vs. 65 or older)
- 7.2 Following randomization, insurance pre-authorization will be obtained for the specified treatment modality. If a patient's insurance will not cover payment for the assigned treatment arm, that patient will be removed from the study and will be treated off protocol.
- 7.3 Radiation target definition for glioblastoma as follows. GTV defined as tumor cavity and any T1 tumor enhancement. CTV will include GTV + 2 cm margin customized to include FLAIR enhancement (if thought by the radiation oncologist to be tumor) and exclude bone, fascia, and other anatomical barriers. PTV-50 will include CTV + 3-5 mm and will be treated to 50 Gy in 30 fractions. PTV-60 boost volume will include GTV + 3-5 mm and will be treated to 60 Gy in 30 fractions.
- 7.4 For patients randomized to IMRT, treatment will be planned using Pinnacle software system. Planning will be based on non contrast CT images obtained at time of simulation in addition to MRI scan. Treatment will be delivered using linear accelerator. Fractionated radiation will be delivered daily M-F with weekends off for all patients. IMRT plans use a configuration of five to seven isocentric 6-MV photon beams delivered in a step-and-shoot technique. For inverse planning specified dose constraints are given to organs at risk including the brainstem, spinal cord, optic chiasm, optic nerves, and cochlea.

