- 10.2.4 At each two month interval follow up visit out to 2 years all six prespecified cognitive test variables will be assessed. The pattern of cognitive change in memory, executive function, and processing speed will be assessed at each time point. The composite cognitive function

score will be determined by averaging standardized Z-scores from all pre-specified cognitive test variables (5 out of 6 are required to calculate a composite score).

- 10.2.5 MRI imaging including diffusion weighted images (DWI) and reconstructed apparent diffusion coefficient (ADC) maps will be analyzed for differences between pre- and post-treatment scans. They will also be analyzed for differences between the two treatment modalities.
- 10.2.6 Diffusion tensor imaging (DTI) will be analyzed for correlation to the cognitive changes and for differences between the two treatment modalities.
- 10.2.7 Pre-treatment factors of RPA class and MMSE will be assessed for predictive determination of local and distant control and cognitive outcome in each treatment arm.
- 10.2.8 Assessment will be made for correlation between location of primary lesion, total volume of intracranial disease, and cognitive outcome for each of the treatment arms.
- 10.2.9 The relationship between MGMT promoter methylation status and cognitive and local control outcomes will be assessed.
- 10.2.10 Post treatment side effects will be recorded at each follow up visit out to two years. Toxicity will be recorded according the Common Terminology Criteria for Adverse Events v4.0.3 for Nervous System Disorders. Only grade 3 and above toxicity that is directly related to therapy will be required to be documented. Pretreatment symptoms should not be considered as toxicity related to the treatment and are not required to be documented unless the symptoms worsen as a result of therapy.
- 10.2.11 Dosimetric parameters such as dose to the hippocampus will be analyzed for relationship with cognitive and local control outcomes.
- 10.3 Evaluation of correlative markers
 - 10.3.1 Genetic markers: DNA will be extracted within the first five fractions of treatment in the laboratory of the Study Chair. Apo E (i.e., Apo E2, Apo E3, and Apo E4) genes will be analyzed for single nucleotide polymorphisms (SNPs) either by Taqman or direct sequencing.

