14.0 Reporting Requirements

14.1 Radiation using either photon or proton technique has known associated risks, including tumor swelling, neurological decline, edema, and radiation necrosis. Nonetheless, radiation is considered standard of care. Adverse treatment reactions will be reported to the IRB. Standard monitoring procedures as noted above to detect and treat postoperative complications will be followed.

- 14.2 All attempts will be made to preserve patients' confidentiality. Patient records will be kept electronically or in secure file cabinets and handled only by responsible personnel.
- 14.3 Study progress and analyses of safety data will be presented to the MDACC DSMB on an annual basis, or as requested.

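### Required toxicity capture covers only the CTCAE nervous-system category at visits after radiotherapy, leaving hearing, vision, endocrine and on-treatment effects with no specified systematic record for the IMPT versus IMRT comparison

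*Combined protocol and SAP*

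**What the plan says.** **Objective.** Section 3.2.10: "To document and descriptively compare post-treatment adverse side effects between the two treatment arms". It sets no organ limit, but it does limit the period to after treatment.

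**Capture rule.** Section 10.2.10 fixes the timing: "Post treatment side effects will be recorded at each follow up visit out to two years". It fixes the category: "Toxicity will be recorded according the Common Terminology Criteria for Adverse Events v4.0.3 for Nervous System Disorders". It then sets a threshold: "Only grade 3 and above toxicity that is directly related to therapy will be required to be documented".

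**Visits.** Section 9.1 schedules clinical examinations every two months for 24 months once radiotherapy has ended, within 30 days either way. It notes that the first evaluation will often come about 4 weeks after radiotherapy.

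**Organs the plan treats as relevant.** Section 7.4 sets dose constraints for organs at risk "including the brainstem, spinal cord, optic chiasm, optic nerves, and cochlea", and section 7.5 applies constraints for IMPT in the same way. The background (section 4.0) reports from a modelling study of childhood brain tumors: "Specific advantages included decreased IQ loss, less cochlea damage, and decreased endocrine effects".

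**Analysis and oversight.** Section 12.4 tabulates adverse events by arm, grade and relationship. Section 13.2 has the research nurse collect data before, during and after treatment. Section 14.1 sends adverse treatment reactions to the IRB and adds: "Standard monitoring procedures as noted above to detect and treat postoperative complications will be followed". Section 14.3 gives the DSMB safety analyses annually or on request.

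**The concern.** A table of adverse events can compare arms systematically only on what both arms were required to record. Here the recording rule is narrower than the objective it serves, in the organs covered. The visit schedule also leaves the treatment period without a defined toxicity record.

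This matters because the arms differ in how dose reaches normal tissue. Section 5.1 says that, given the higher cost of IMPT, it is important to show whether there is a measurable clinical benefit. The optic structures, the cochlea and endocrine function are places where the plan's own text suggests the arms could differ. Early effects such as the swelling and edema listed in section 14.1 could arise and settle before the first scheduled entry. At stake is the completeness of a secondary, descriptive comparison and of the safety data that reach the DSMB.

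**Working it through.** The plan gives no toxicity figure to reproduce, and nothing is sized on toxicity. The check is a side-by-side reading plus one interval.

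**Organs.**
- Objective (3.2.10): side effects, no organ limit.
- Capture (10.2.10): one CTCAE category.
- Analysis (12.4): adverse events, no category limit.
- Hearing and vision: cochlea and optic structures are dose-constrained (7.4, 7.5), but no hearing or vision toxicity is defined.
- Endocrine: serum hormones are assayed in both arms at the start of treatment and at each follow-up visit (10.3.3). Section 12.4 uses them only as predictors of neurocognitive decline, not as an outcome compared between arms.
- Blood: concurrent temozolomide is mandatory (6.10) and a blood count is taken at baseline (8.3), but no later blood toxicity is specified.

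The capture rule is therefore the narrowest of the three statements, and the table in 12.4 inherits its limits.

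**Time to the first scheduled toxicity entry.** Inputs: 30 fractions (7.3), Monday to Friday (7.4, 7.5); first evaluation often about 4 weeks after radiotherapy, otherwise at 2 months ± 30 days (9.1). Assumptions: a Monday start, no breaks, and 2 months = 61 days.
- First to last fraction: 5 full weeks plus Monday to Friday = 5 × 7 + 4 = 39 days.
- Visit at 4 weeks: 39 + 28 = 67 days.
- Visit at 2 months, earliest: 61 − 30 = 31; 39 + 31 = 70 days.
- Visit at 2 months, latest: 61 + 30 = 91; 39 + 91 = 130 days.

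The range is 67 to 130 days, or about 10 to 19 weeks (67/7 = 9.6; 130/7 = 18.6).

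**Does another section fill that interval?**
- 13.2 says treatment-period data are collected, but gives no toxicity content, grading or schedule.
- 14.1 sends reactions to the IRB. That is reporting of events that come to notice, not a graded record kept alike in both arms.
- 14.1 also relies on monitoring described earlier. Section 9 does describe procedures, but its clinical examinations and imaging (9.1, 9.3) are scheduled after radiotherapy. Medication recording (9.4) and documentation of extra evaluations (9.5) have no stated on-treatment schedule.

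These sections leave the on-treatment scope undefined. They do not show that nothing is collected.

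**The case against.** The strongest reply is that the plan is broader than 10.2.10 alone.
- Treatment-period data are collected (13.2), reactions go to the IRB without an organ or period limit (14.1), and unscheduled follow-ups are documented (9.5).
- Steroid doses (9.4) and serial MRI (9.3) bear directly on edema. Symptom and quality-of-life questionnaires are completed at each follow-up visit (10.2.3).
- Objective 3.2.10 is itself limited to post-treatment effects, so on the time axis 10.2.10 matches it.
- The comparison is secondary and descriptive.

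Much of this stands, and it rules out several stronger readings.
- A reader might infer that all on-treatment toxicity is lost. The documents show an unspecified scope, not proven absence. History at the first visit may also recover earlier events.
- A reader might infer that the plan names visual effects, or that hearing and endocrine effects are trial hypotheses. It names optic structures only as dose-constrained organs. The hearing and endocrine effects are background from paediatric modelling.
- A reader might infer that a real difference would be reported as no difference, or that the DSMB would be blind. An outcome that is not collected goes unreported, and the DSMB may request analyses.
- A reader might take the one-third over-accrual in 12.2 as patients without toxicity data. Evaluability there depends on receiving assigned treatment and completing cognitive testing, not on attending clinic.

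What the reply does not supply is a systematic two-arm record outside the nervous-system category or during the 30 fractions. Extending the record to the treatment period does widen objective 3.2.10, and that should be done openly.

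**Conclusion.** The point holds as a gap in specification. Section 10.2.10 gives hearing, vision and endocrine toxicity no required entry, and the plan sets out no systematic on-treatment toxicity record. The first scheduled entry comes about 67 to 130 days after the first fraction. That interval is the wait for a scheduled entry, not a period in which every event is lost. Differences between arms in these effects may go unreported, and the DSMB has no specified data on them. How many events are involved cannot be estimated from the documents. The primary cognitive endpoint, its sample size and its analysis are not affected.

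The conclusion rests on two assumptions. First, the category named in 10.2.10 is meant as a limit and does not contain the hearing, visual and endocrine terms. The CTCAE term lists are not in the documents, so if those terms are meant to be included, the section should say so. Second, the interval assumes 30 uninterrupted weekday fractions from a Monday.

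**What to change.** 1. In 10.2.10, add the CTCAE eye, ear and endocrine categories, and blood because concurrent temozolomide is mandatory, at the visits already scheduled.
2. In 10.2.10, state that the toxicity record starts at the first fraction and is entered by the research nurse who already collects treatment data (13.2).
3. Align the other sections with that scope. Objective 3.2.10 should cover on-treatment and post-treatment effects, the tabulation in 12.4 should name the categories and period, and 14.1 should point to this record in place of its reference to postoperative complications.

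**Cost.** Protocol wording, a longer toxicity form and more data entry. No tests or visits are added, provided events can be noted while patients attend for daily treatment. For the same reason, only clinically apparent events would be captured. The existing filter (grade 3 or above and directly related to therapy) would still apply to the added categories unless it is changed separately.
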